#### **4.6 Duration of Therapy**

Patients may continue on ibrutinib maintenance therapy up to 4 years in the absence of disease progression or development of unacceptable toxicity; or patient preference (withdrawal of consent). Clinical suspicion of progressive disease (PD) or loss of response should be investigated radiographically, and will result in removal of active therapy if confirmed by clinical investigation.

#### **4.7 Duration of Follow Up**

Patients who complete 4 years of maintenance therapy with ibrutinib will have one final follow-up study visit approximately 30 days post-last dose. Patients who discontinue study therapy prior to this point will be followed up to a maximum of 4 years (post-first dose of treatment) for survival endpoints (including date of progression). Follow-up will occur every 3 months (up to 2 years after the first dose of treatment) and then every 6 months thereafter (up to 4 years post-first dose).

#### **4.8 Removal of Patients from Therapy and/or Study as a Whole**

Patients can be removed from the study treatment (follow-up permitted) and/or from the study as a whole (no follow-up permitted) at any time at their own request, or they may be withdrawn at the discretion of the investigator for safety, behavioral or administrative reasons. The reason(s) for discontinuation must be documented on the appropriate eCRF and may include:

- Patient voluntarily withdraws from *treatment* (follow-up continues)
- Patient withdraws *consent* (termination of treatment *and* follow-up)
- Patient is *unable to comply* with protocol requirements (termination of treatment, follow up continues)
- Patient demonstrates *disease progression* (termination of treatment, follow-up continues). Clinical suspicion of progressive disease (PD) or loss of response should be investigated radiographically, and will result in removal of active therapy if confirmed by clinical investigation.

Study Numbers: NU 14H06  
PCI-32765MCL2003

Initial version: September 24, 2014  
AMD 11: ver. date 08.06.2022

- Patient experiences *toxicity* that makes continuation in the protocol unsafe (termination of treatment, follow up continues)
- Treating physician determines that continuation on the study would *not be in the patient's best interest* (termination of treatment, follow up continues)
- Patient becomes *pregnant*, see section 7.2.6 for reporting timeframe (termination of treatment, but follow up continues)
- Patient develops a second malignancy (except for basal cell carcinoma or squamous cell carcinoma of the skin) that requires treatment, which would interfere with this study (termination of treatment, but follow up continues).  
NOTE: Patients who stop treatment in order to receive other anti-cancer therapy for a second malignancy may, on a case-by-case basis and upon approval of PI and DMC, be considered for possible re-start of study medication once other anti-cancer therapy is complete. See Section 4.3.1 for more details.

## 5.0 STUDY PROCEDURES

Table: Schedule of Events

Test/Assessment	Pre-Study	Screening	On-Treatment 		Off-Treatment	
		Baseline Tests 	Cycles 1-6 	Cycles 7+ 	EOT 	Follow-Up 
Documentation of induction chemotherapy 	X					
Informed consent		X				
Medical history		X				
Concomitant medications		X	X	X		
Physical exam 		X	X	X	X	
ECOG status		X	X	X		
Hematology 		X	X	X	X	
Chemistries 		X	X	X	X	
Pregnancy test 	X					
Hep B & C serologies 		X				
Tissue for research 		X				
Research blood samples 			X	X		
CT scan (C/A/P) or MRI 		X	X	X 		
Peripheral blood for flow cytometry 			X	X		
Bone marrow biopsy 		X		X		X 
EGD/Colonoscopy 		X		X		X 
Drug administration & accountability 			X			
Adverse events 		X	X	X	X	X
Survival					X	X

Must include at least 4 cycles of R-CHOP (with or without alternating R-DHAP), R-Hyper-CVAD, or bendamustine + rituximab (all with or without auto SCT). Last dose of cytotoxic chemotherapy must be at least 14 days prior to registration (but no more than 120 days prior). Patients who underwent auto SCT must show engraftment and meet all required baseline hematological parameters.

While on treatment, one cycle will be defined as 28 days (+/- 2 days). Assessments will occur on day 1 of each cycle ( $\pm$  2 days, for the first 6 months), then every 3 cycles ( $\pm$  10 days, up to 4 years). If after 2 years a patient is clinically stable and lives far from the study site, he or she may elect to be seen every 6 cycles ( $\pm$  10 days), with a sufficient drug supply, as detailed in section 4.2. Labs should be resulted prior to treatment to assess the need for dose modifications (see section 4.3 for details). When a dose is missed or held, it will not be made up, regardless of duration. Observations and scheduled assessments will continue regardless of amount of drug the patient has had, and should always be based on time from C1D1. Please contact QA if you have any questions on timing of holds or study assessments.

CBC with platelets/differential

Comprehensive chemistry panel, Mg, and LDH. Comprehensive chemistry panel includes glucose, calcium, albumin, ALT, AST, sodium, potassium, total bilirubin, alk phos, creatinine.

If applicable for WOCBP (urine or serum).

Baseline/screening tests required to be completed as follows: within 90 days prior to registration for imaging, bone marrow biopsy and EGD/Colonoscopy (if applicable) and within 14 days prior to registration for all other baseline assessments (except informed consent, which can be signed within 30 days prior to registration).

Imaging should be performed at baseline, after cycles 3 and 6, every 6 months/cycles for the first 2 years, once at 3 years, and as clinically indicated thereafter (including EOT, as clinically appropriate, for patients who complete 4 years of therapy, or patients that come off study treatment early for a reason other than progression). In general, it is *preferred* that imaging be CT-based; at a minimum, the same modality should be used consistently for each patient.

Ibrutinib will be administered at a dose of 560 mg PO daily throughout the course of treatment unless a dose reduction occurs (see section 4.3.2 for details).

Patients will be asked to keep a study calendar for the duration of treatment See section 4.2 for details on dispensing and visit frequency.

Patients will be evaluated on Day 1 of each cycle ( $\pm 2$  days) for the first 6 cycles (prior to the start of each cycle). NOTE: Cycle 1 Day 1 should begin within 14 days after registration, however Day 1 labs (hematology and chemistry tests) need only be repeated if screening labs were performed  $>7$  days prior to C1D1.

Patients will be evaluated every 3 cycles (on Day 1,  $\pm 10$  days) beginning with cycle 7. After 2 years on therapy, patients will continue to be seen *clinically* every 3 cycles, however collection of data for study purposes will only be required every 6 cycles (approximately every 6 months) for the remainder of study treatment.

**Patients who complete 4 years** of maintenance therapy with ibrutinib will have one final follow-up study visit approximately 30 days post-last dose. **Patients who discontinue study therapy prior to this point** will be followed up to a maximum of 4 years (post-first dose of treatment) for survival endpoints only (no labs or physical exam are required), including date of progression. Follow-up will occur until progression at the following times: every 3 months ( $\pm 10$  days) up to 2 years after the first dose of treatment and then every 6 months ( $\pm 10$  days) thereafter up to 4 years after the first dose of treatment.

Physical exam includes height (baseline only), weight, 12-point symptom assessment and vitals (bp, heart rate, temperature)

Bone marrow biopsy is only required (within 90 days of registration) for those with documented bone marrow involvement of MCL at time of last bone marrow biopsy. These patients should have repeat bone marrow biopsy after 6 cycles of therapy, in order to judge efficacy of treatment, then as clinically indicated during the period of follow up. If no previous bone marrow biopsy was obtained (e.g. at time of diagnosis), or if disease involvement was resolved as of most recent bone marrow biopsy, then none is required for trial entry, however it may be done at the discretion of the treating investigator.

Only required (within 90 days of registration) for those with documented involvement of MCL by EGD and/or colonoscopy, at time of last EGD/colonoscopy.

These patients should have repeat EGD/colonoscopy with biopsy after 6 cycles of therapy, in order to judge efficacy of treatment, then as clinically indicated during the period of follow up. If no previous EGD/colonoscopy was obtained (e.g., at time of diagnosis), or if disease involvement was resolved as of most recent EGD/colonoscopy with biopsy, then none is required for trial entry, however it may be done at the discretion of the treating investigator.

At screening, patients will have HepBcAb, HepBsAg, and HepC Antibody. Carriers of hepatitis B should be closely monitored for clinical and laboratory signs of active HBV infection and for signs of hepatitis during and for several months following ibrutinib treatment. Specifically, those with negative HBsAg and undetectable viral load should have these parameters rechecked approximately every 2-3 months while on ibrutinib and until 6 months after stopping ibrutinib. Any emerging HBsAg positivity, or rising viral load, should prompt interruption of drug and consultation with hepatology. Those with positive HBsAg and/or detectable viral load at time of enrollment should be seen by a hepatologist prior to starting study therapy, and HBV prophylaxis should be strongly considered.

Adverse events will be tracked from time of signed informed consent until completion of the last study-related procedures (which may include contact for follow-up safety). Serious adverse events will be reported for 30 days beyond cessation of study treatment. AE's resulting in discontinuation will be followed until resolution, or until patients start subsequent therapy, whichever comes first.

Peripheral blood samples for exploratory studies (1 x 10 ml EDTA tube) will be collected cycle 1 day 1 (pre-dose), cycle 2, and cycle 7, and at approximately 18-24 months post-first dose of study drug. A second peripheral blood sample should be obtained at the same time as each research sample, and sent for flow cytometry, as standard of care, to be performed at the treating institution. Another sample (1 x 6mL EDTA tube) will be collected and stored for future use at each time point. Please see Section 9.0 for further details.

Tissue (3-5 unstained FFPE slides) from a prior biopsy will be obtained at baseline from all patients (for whom such tissue is available – lack of availability will not disqualify patients from participating, but it is not *optional* for those who do have available tissue). See Section 9.0 for more details.

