##### 3.1.2 Patients must have received 4 or more cycles of one of the following prior systemic induction chemotherapy regimens:

- R-CHOP (with or without cytarabine-containing cycles, including "Nordic" and MCL-NET protocols) [1, 2] with or without auto SCT
- R-Hyper-CVAD with or without auto SCT
- Bendamustine + rituximab with or without auto SCT

*Please note:*

- *Patients are allowed to receive combinations of the above regimens*
- *At the time of registration, patients must be at least 14 days out from last dose of cytotoxic chemotherapy, but no more than 120 days. If a patient underwent auto SCT, he/she must demonstrate engraftment (per treating investigator's discretion) and meet all other hematological requirements as outlined in 3.1.8 below.*
- *Patients who progress during induction therapy are not eligible to enroll in this study.*

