##### 3.1.3 Patients must have achieved a response to induction chemotherapy (either CR or PR by Cheson 2007 criteria) and be without known progression.

##### 3.1.4 Patients *may* have received prior radiotherapy.

Study Numbers: NU 14H06  
PCI-32765MCL2003

Initial version: September 24, 2014  
AMD 11: ver. date 08.06.2022

- 3.1.5 Patients must be age  $\geq$  18 years.
- 3.1.6 Patients must exhibit an ECOG performance status  $\leq$  2.
- 3.1.7 Patients must demonstrate adequate organ and marrow function (as defined below) documented within 14 days of registration:
  - ANC  $\geq$  1000/mm^3, independent of growth factor support
  - Platelets  $\geq$  100,000/mm^3, or  $\geq$  50,000 in cases of ongoing bone marrow involvement (*In either case, these must be independent of transfusion support*)
  - Total bilirubin  $\leq$  1.5 x upper limit of normal (ULN)
  - AST(SGOT)/ALT(SPGT)  $\leq$  3 x ULN
  - Creatinine clearance  $\geq$  25 ml/min (using the Cockcroft-Gault Equation – See Appendix III)

*Please note: Patients who do not meet the above criteria because of Gilbert's Syndrome are still eligible.*

- 3.1.8 Women of child-bearing potential (WOCBP) and men must agree to use adequate contraception (see below 'NOTE" for details) prior to study entry and for the duration of study participation (see timelines below for women and men). In addition, men must agree not to donate sperm during and after study participation. Should a woman become pregnant or suspect she is pregnant while participating in this study, she should inform her treating physician immediately.

*NOTE: For female patients, these restrictions apply for 1 month after the last dose of study drug. For male patients, these restrictions apply for 3 months after the last dose of study drug.*

*NOTE: A female of child-bearing potential is any woman (regardless of sexual orientation, having undergone a tubal ligation, or remaining celibate by choice) who meets the following criteria:*

- Has not undergone a hysterectomy or bilateral oophorectomy; or
- Has not been naturally postmenopausal for at least 12 consecutive months (i.e., has had menses at any time in the preceding 12 consecutive months).

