#### 6.2.2 Rate of conversion from PR to CR

Progression will be evaluated using Cheson 2007 criteria (Revised Response Criteria for Malignant Lymphoma, modified). Patients must have already achieved either PR or CR during induction chemotherapy prior to enrolling in this study. Patients with measurable disease at time of enrollment will have it followed with imaging. Only patients who had a PR at the time of registration and who complete  $\geq 1$  complete cycle of ibrutinib maintenance therapy will be evaluable for this endpoint. Please refer to appendices for a summary of Cheson criteria.

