#### **10.3.2 Secondary Objectives**

To assess toxicity, all adverse events will be summarized as to type, severity, frequency, timing and attribution. Descriptive frequencies and proportions will be used for this analysis.

To determine rates of conversion from PR to CR, only patients who had a PR at the time of registration and who complete  $\geq 1$  complete cycle of ibrutinib maintenance therapy will be evaluable for this endpoint. These rates will be calculated as a proportion together with exact 90% confidence limits.

To determine median overall survival (OS) after 4 years, Kaplan-Meier curves will be determined for overall survival and the five-year point on this curve, along with 90% confidence limits, will be determined. Patients will be evaluated monthly for the first 6 months on treatment, then every 3 months thereafter. Patients who go off treatment will continue to be followed for survival up to a maximum of 4 years post-first dose. Follow-up will occur every 3 months (up to 2 years after the first dose of treatment) and then every 6 months thereafter (up to 4 years post-first dose).

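### The baseline disease assessment may predate the last induction dose, so the PR-to-CR rate can count responses to induction as conversions on ibrutinib

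*Combined protocol and SAP*

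**What the plan says.** Four parts of the plan bear on this point.

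- **Baseline window.** Section 5.0, footnote 6, allows the disease assessments "within 90 days prior to registration for imaging, bone marrow biopsy and EGD/Colonoscopy (if applicable". Footnotes 13 and 14 repeat the 90 days for marrow and endoscopy. Other baseline tests have a 14-day window, apart from consent at 30 days.
- **End of induction.** Section 3.1.2 says that "patients must be at least 14 days out from last dose of cytotoxic chemotherapy, but no more than 120 days" at registration. Section 5.0, footnote 1, agrees: "Last dose of cytotoxic chemotherapy must be at least 14 days prior to registration (but no more than 120 days prior". For transplanted patients, 3.1.2 adds "If a patient underwent auto SCT, he/she must demonstrate engraftment" and the blood-count criteria. It does not ask for restaging.
- **Response at entry.** Section 3.1.3: "Patients must have achieved a response to induction chemotherapy (either CR or PR by Cheson 2007 criteria) and be without known progression". It does not say when that response must be assessed.
- **Conversion endpoint.** Section 10.3.2 evaluates "only patients who had a PR at the time of registration and who complete" at least one full cycle of ibrutinib, and 6.2.2 says the same. On the analysis, 10.3.2 says: "These rates will be calculated as a proportion together with exact 90% confidence limits". Neither section says which assessment fixes PR status at registration.

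The first on-treatment scan is due after ibrutinib cycle 3 (footnote 7).

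**The concern.** A conversion rate compares disease status before and after the start of ibrutinib. The comparison is clean only if no other active treatment falls between the two assessments. Here the limit on the age of the scan is longer than the minimum gap since chemotherapy, so some induction can fall between them. A CR achieved by that induction would first be documented at the cycle 3 scan and would be recorded as a conversion on study.

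With no control arm, nothing offsets the error, and it runs in one direction. The denominator is only the PR subset of 36 evaluable patients, so a handful of misclassified patients would move the proportion. What is at stake is the reading of one named secondary endpoint (Section 2.2.2).

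**Working it through.** The plan gives no target rate, sample size or power for the conversion endpoint, so there is no figure of its own to reproduce. The check is date arithmetic, with registration as day 0.

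**Inputs**
- Baseline disease assessment: day −90 to day 0 (5.0, footnote 6).
- Last cytotoxic dose: d days before registration, d from 14 to 120 (3.1.2; 5.0, footnote 1).
- First ibrutinib dose: within 14 days after registration (4.1; 5.0, footnote 9).
- Induction cycle length: not stated; assumed 21 or 28 days, with cytotoxic treatment on the first day of each cycle.

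**Step 1. Longest lead of the baseline over the last dose = max(0, 90 − d)**

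| d (days) | Longest lead (days) |
|---|---|
| 14 | 76 |
| 30 | 60 |
| 45 | 45 |
| 60 | 30 |
| 76 | 14 |
| 90 to 120 | 0 |

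The longest interval from baseline to the first ibrutinib dose is 90 + 14 = 104 days.

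**Step 2. How much induction fits in the extreme case.** Take a scan on day −90 and the last dose on day −14.
- 21-day cycles start after the scan on days −77, −56, −35 and −14: four cycles.
- 28-day cycles start on days −70, −42 and −14: three cycles.

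The extreme has a limit of its own. A patient given only the minimum four 21-day cycles would have been scanned on day −90 before any induction and could not show a PR. The full 76 days therefore needs a longer induction.

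**Step 3. A compliant example.** Six 21-day cycles start on days −119, −98, −77, −56, −35 and −14. A scan on day −79, after two cycles, shows PR. It meets footnote 6, and 3.1.2 is met on cycle count and on timing. It precedes the last dose by 79 − 14 = 65 days, with four cycles still to come. If no later assessment is made, the next required scan is after ibrutinib cycle 3, 3 × 28 = 84 days after the first dose. A CR reached in those four cycles is first seen there.

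**Step 4. Direction of the bias.** Let f be the share of PR patients assessed before the end of induction, q the share of those who reach CR from the remaining induction, and t the true conversion rate on ibrutinib, taken as the same in all others. Then

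observed rate = f[q + (1 − q)t] + (1 − f)t = t + fq(1 − t).

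The added term is never negative. The documents give no value for f, q or t. Purely to show how the formula behaves, assume f from 10% to 50% and q from 20% to 40%:
- t = 0: observed 0.10 × 0.20 = 2% up to 0.50 × 0.40 = 20%.
- t = 20%: observed 20% + 0.02 × 0.80 = 21.6% up to 20% + 0.20 × 0.80 = 36%.

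These are not estimates for this trial.

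**Step 5. Primary endpoint.** The rule of 26 or more of 36 (10.2) counts patients alive without progression and does not use PR or CR status. Its exact type I error at 60% is 0.0904 and its power at 80% is 0.911, consistent with the stated 10% and 90%. Nothing here changes it.

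**The case against.** The best defence is that the plan's intent is plain. Section 1.3 describes patients in CR or PR after intensive induction. Section 4.1 asks for four or more cycles with a documented response. Sections 6.2.2 and 10.3.2 take PR status at registration, and footnotes 13 and 14 look to the latest marrow or endoscopy. On that reading, a patient known to be in CR at the end of induction is not in the PR denominator, and the error arises only if a site has no later assessment or disregards one. That shows what was meant, and sites that restage after induction are not affected. It does not make restaging mandatory: the one baseline scan required may be older than the last dose.

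Other parts of the defence stand and limit the point:
- For transplanted patients, engraftment and the count thresholds of 3.1.7, free of growth factor and transfusion support, make a gap of only 14 days unlikely. Their lead is probably shorter than 76 days, although a pre-transplant scan remains acceptable.
- The conversion rate has no hypothesis, threshold or decision attached. Being uncontrolled, it could not separate ibrutinib from a continuing response to induction even with a perfectly timed scan.
- Consent may be signed no earlier than 30 days before registration, so scans from day −90 to day −31 are routine scans made before consent. Requiring a later one is not free.

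A reader might go further and infer that baselines are typically 76 days out of step, that a known part of the conversion rate is artefact, or that the PFS result is compromised. The documents support none of these: 76 days is the extreme of two windows, the number of PR patients and the share scanned early are not given, and the primary rule does not depend on response category.

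**Conclusion.** The point holds as a gap in the definition of baseline for one secondary endpoint. The text permits a baseline that predates the last induction dose, and patients treated to the letter can be scored as converting because of induction. The possible lead runs from 0 to 76 days according to the date of the last dose.

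The direction of the bias is upward; its size cannot be estimated from the documents. The conclusion rests on the windows as written and on no later restaging being done in the affected patients. The lead in days needs no assumption about cycle length; only the translation into cycles does. The remedy removes one contributor to the rate and would not make conversion attributable to ibrutinib.

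**What to change.** **Section 5.0, footnote 6** (with footnotes 13 and 14): keep the 90-day limit and add that baseline disease assessments used to classify PR or CR must follow the last induction dose and any transplant. This helps only patients still to be enrolled; the documents, now at Amendment 11, do not say whether there are any.

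**Section 10.3.2**: keep the planned PR-to-CR rate, with its planned denominator and exact 90% limits, as the main result. Replacing that population after patients have been enrolled would be hard to defend. Add a sensitivity analysis limited to patients whose baseline assessment followed the last induction dose or, if transplanted, the transplant. Report how many PR patients did not meet this. The date of the last dose is already needed to check eligibility, so comparing it with the assessment date should need little or no new data.

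**Cost**: a later or repeat baseline scan (or marrow or endoscopy, where these apply) for patients assessed early, and a smaller denominator with wider limits in the sensitivity analysis. The sample size and the 26-of-36 rule do not change.

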## **10.2 Sample Size and Power Calculations**

The primary endpoint is three-year PFS. Our null hypothesis is that ibrutinib maintenance will yield no improvement upon the 60% three-year PFS observed in

studies described above. We consider an observed three-year PFS of 80% both feasible and of significant clinical improvement. The study will have 10% Type I error and 90% power to detect an effective treatment using a one-stage design based on the true proportion of patients achieving 3-year PFS is at least 80% versus the null hypothesis that the true complete response rate is at most 60%.

Based upon these parameters, our sample size will be 36 evaluable patients. For the final analysis, if 25 or fewer patients are alive and without progression from among all 36 evaluable patients accrued, we will consider this regimen ineffective for this patient population. If, on the other hand, 26 or more patients are alive and without progression, this will be considered sufficient evidence that this treatment may be recommended for further testing in subsequent studies, particularly in a randomized setting.

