### **10.3 Planned Analyses**

#### **10.3.1 Primary Objective**

The primary objective will be to determine the progression-free survival (PFS) rate after 2 and 3 years. This will be done in two ways. First, the proportion of patients alive and progression-free at 2 and 3 years will be calculated, along with an exact 90% confidence interval, both two-sided as well as a lower 90% confidence limit. The number of patients alive and progression-free at 2 and 3 years will be used to address the primary hypothesis as indicated in section 10.2 above. In addition, a Kaplan-Meier curve will be calculated to obtain the actuarial estimate of two-year progression-free survival.

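### Patients who stop ibrutinib without progression have no clearly scheduled objective disease assessment, and the plan has no rule for counting those unassessed near 3 years, so the primary count can be inflated.

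*Combined protocol and SAP*

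**What the plan says.** **Follow-up off treatment.** Section 4.7 and footnote 11 of the Schedule of Events (section 5.0) set contacts every 3 months to 2 years after first dose, then every 6 months to 4 years. Footnote 11 limits the content: "for survival endpoints only (no labs or physical exam are required), including date of progression".

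**Imaging.** In the Schedule of Events the CT/MRI row is marked at Screening, Cycles 1-6 and Cycles 7+, and is blank under EOT and Follow-Up. The marrow and endoscopy rows do carry a Follow-Up mark, for use as clinically indicated in patients with earlier involvement. Footnote 7 sets scans after cycles 3 and 6, six-monthly to 2 years, once at 3 years, and later as clinically indicated. It mentions an EOT scan, where clinically appropriate, for groups that include "patients that come off study treatment early for a reason other than progression".

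**Endpoint.** Section 6.1 judges progression by Cheson 2007 and has it documented by imaging when disease is measurable.

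**Test.** Section 10.2 declares the regimen ineffective "if 25 or fewer patients are alive and without progression from among all 36 evaluable patients accrued". Section 10.3.1 adds: "The number of patients alive and progression-free at 2 and 3 years will be used to address the primary hypothesis". Its other estimate stops short of the primary time point: "a Kaplan-Meier curve will be calculated to obtain the actuarial estimate of two-year progression-free survival".

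No section says how to count a patient whose disease was not assessed near 3 years.

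**The concern.** Section 4.8 foresees several ways off treatment without progression, with follow-up continuing: toxicity, patient choice, inability to comply, physician decision, pregnancy and second malignancy. For these patients the plan asks for a progression date without clearly scheduling the assessment that would establish one. Ascertainment is therefore weaker off treatment than on it.

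The primary statistic is a count with a fixed denominator and no censoring. A progression that is missed, or dated after 3 years because it was found late, leaves the patient on the success side. The error runs one way only, and a single-arm trial has no control group in which the same error would offset it. With 36 patients and a one-patient margin between the two conclusions, a small number of missed events matters.

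**Working it through.** **1. Reproduce the design.** Section 10.2 states "The study will have 10% Type I error and 90% power to detect an effective treatment using a one-stage design", with 60% as the null and 80% as the target 3-year PFS, and "our sample size will be 36 evaluable patients"; success needs at least 26. With X binomial (36, p):
- P(X ≥ 26 | p = 0.60) = 0.0904.
- P(X ≥ 26 | p = 0.80) = 0.9111.

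Both meet the stated 10% and 90%, so the design is reproduced.

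**2. Width of the margin.** The exact one-sided 90% lower limit is the 0.10 quantile of Beta(x, 37 − x):
- 26/36: 60.5%, just above the null.
- 25/36: 57.6%, below it.

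One patient changes the conclusion.

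**3. Effect of k missed progressions.** If k patients who have progressed are counted as successes, the rule passes when the true count is at least 26 − k. At p = 0.60:
- k = 0: 0.090
- k = 1: P(X ≥ 25) = 0.162
- k = 2: P(X ≥ 24) = 0.262
- k = 3: P(X ≥ 23) = 0.384

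This step needs no assumed stopping rate.

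**4. Effect under assumed rates.** The documents give no 3-year rate of stopping without progression and no rate of missed events. The only related figure is in section 1.2.3: 32 of 392 patients (8.2%) in other ibrutinib studies stopped for an adverse event. It is not a 3-year maintenance rate and covers one reason for stopping. Assumptions:
- true 3-year PFS is 60% with constant hazard, −ln(0.60)/3 = 0.1703 per year;
- a share d of all patients stops event-free at time t (1 to 2 years);
- a share m of their later events, up to 3 years, is missed or dated too late.

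Remaining risk to 3 years after stopping at t is r = 1 − exp(−0.1703 × (3 − t)): 28.9% at t = 1, 22.5% at t = 1.5 and 15.7% at t = 2.

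Apparent 3-year PFS = 0.60 + d × r × m. For d = 20%, t = 1, m = 50%: 0.60 + 0.20 × 0.289 × 0.50 = 0.629, and P(X ≥ 26 | 0.629) = 0.162. The same steps give these ranges, from t = 2 to t = 1:

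| d (stop early) | m (missed) | Apparent PFS | False-positive rate |
|---|---|---|---|
| 8.2% | 25% | 60.3-60.6% | 9.7-10.3% |
| 8.2% | 50% | 60.6-61.2% | 10.4-11.6% |
| 20% | 50% | 61.6-62.9% | 12.5-16.2% |
| 30% | 50% | 62.3-64.3% | 14.6-20.9% |

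These are upper-side values for the chosen d and m. The formula treats every later PFS event as one that could be missed, but some are deaths, which follow-up records.

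**5. Cost of the opposite convention.** If 10% of patients are unassessed, independently of outcome, and are counted as failures, the success probability at a true 80% is 0.80 × 0.90 = 0.72 per patient. P(X ≥ 26 | 0.72) = 0.572, against 0.911 as designed.

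**The case against.** The strongest reply is that follow-up is active. Date of progression is a required item in the study schema, section 4.7 and footnote 11, at fixed contacts until progression. Deaths are captured, symptomatic relapse would probably surface at a contact, and the EOT visit carries an exam and laboratory tests. All of this stands. A reader might infer that progression off treatment is known only by chance; the documents do not support that. What is missing is a clearly scheduled objective assessment.

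Footnote 7's 3-year scan, and its later imaging as clinically indicated, are not limited in words to patients on treatment. That also stands, so one cannot say outright that no scan is scheduled. But the table places imaging on treatment only, and sites could reasonably differ.

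A reader might also infer that the plan counts unassessed patients as progression-free. No section says so. It is the literal result of defining PFS as the absence of an event over a fixed denominator, but the plan is silent on unknown status.

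Finally, it is tempting to give early stoppers the full 40% three-year event risk. With 20% stopping and half missed, that yields 0.60 + 0.20 × 0.40 × 0.50 = 0.64 and a false-positive rate of 19.8%. This overstates the effect, because these patients were event-free when they stopped; the remaining-risk calculation gives 12.5-16.2%.

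**Conclusion.** The gap is real and worth closing. Objective assessment after early stopping is not clearly scheduled, table and footnote 7 do not settle whether the 3-year scan applies off treatment, and the primary count has no rule for patients unassessed near 3 years. The resulting error can inflate the 3-year count and cannot lower it; the documents do not establish that it will.

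One missed progression moves the false-positive rate at a true 60% from 9.0% to 16.2%, and two move it to 26.2%. On average the effect depends on rates the documents do not give. It is about 10%, essentially nominal, if 8.2% stop early and a quarter of their later events are missed. It reaches 14.6-20.9% if 30% stop and half are missed. These figures rest on constant hazard, event-free stopping at 1 to 2 years, and assumed stopping and missed shares.

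**What to change.** 1. State whether footnote 7's imaging, including the 3-year scan, applies to patients off treatment without progression, and make the Schedule of Events agree.
2. At each follow-up contact, record on the eCRF the date and result of the latest imaging done in routine care. This does not create an assessment where none was done, but it shows which patients have one.
3. In section 10.3.1, add a 3-year Kaplan-Meier PFS estimate, censored at the last documented disease assessment, beside the 26/36 count.
4. Report the count again with patients lacking a disease assessment near 3 years treated as not progression-free. Label it a worst-case sensitivity analysis.

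The cost is one eCRF field and a little more analysis. Items 2 to 4 add no procedure for patients and leave the sample size and primary rule unchanged. The censored estimate may be lower than the raw proportion, with a wider interval. The worst-case row is severe: with 10% unassessed, power at 80% falls from 91% to 57%, so it must not replace the primary rule.
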